5.5.2. Secondary comparison

- If the primary comparison on interest (Section 5.5.1) using the ITT-E population demonstrates non-inferiority of Q4W compared to Current ART then the following key secondary comparisons using the ITT-E population will be tested: Treatment with Q4W IM will be declared non-inferior to Current ART with respect to the proportion of participants with HIV-1 RNA < 50 copies/mL at Week 48 (defined by the US FDA snapshot algorithm) if the lower end of a two-sided 95% confidence interval for the difference between in rates (Q4W IM– Current ART) lies above -10% using the ITT-E population
- Superiority of Q4W IM compared to Current ART respect to change from baseline in HIVTSQs, at Week 44 using a two-sided 5% level of significance
- Changes in the PIN acceptance score within the CAB LA + RPV LA arm at Week 48 from Week 5 using a two-sided 5% level of significance

There are no planned adjustments for multiple comparisons or multiplicity.

For the primary endpoint treatment comparison at Week 48, no multiple comparison adjustment is necessary for testing non-inferiority followed by superiority (conditional on achieving a significant test for non-inferiority) since testing follows a pre-specified

sequence of hypothesis such that if the first hypothesis tested is not significant, all subsequent tests will not be performed. This fixed sequence procedure controls the type I error rate at the nominal level.

In addition to the primary and the key secondary comparisons, the comparisons between two treatment arms for ACCEPT (general acceptance score), SF-12 (health status), and HATQoL (Life satisfaction) at timepoints through Week 48 will also be performed as supportive analyses.

Lastly, for the IDMC interim analyses, since the statistical stopping guidelines will not result in early stopping for positive efficacy findings, these interim treatment comparisons will not inflate the Type I error rate for the primary treatment comparison.

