10.6. Planned Health Outcomes Statistical Analyses

Statistical Analyses
Endpoints
Change from Baseline in 
 ○ HIVTSQs total treatment satisfaction score at Week 4b, 24, 44 ○ ACCEPT general acceptance score at Week 8, 24, 48 ○ SF-12: Total Score, physical component summary(PCS) and mental component summary(MCS) at week 24, 48 ○ HATQoL (Life satisfaction, HIV medications, disclosure worries) at week 24, 48.
Model Specification

 • An analysis of covariance (ANCOVA) model will be used at each visit at Maintenance phase with covariates: treatment, age (<50, ≥ 50), baseline third agent class, sex at birth, and race (i.e. white, non-white) (as described in 5.4) and baseline score value (as a continuous

variable).
 
 Adjusted point estimates will be derived as LSMEAN S using the observed margins (OM) option within PROC MIXED in SAS. No adjustment for multiplicity will be applied as these analyses will be considered exploratory. Interactions between treatment and each of the covariates will not be assessed unless the exploratory subgroup analyses on the primary endpoint highlights significant interactions. In this situation, the interaction(s) of interest will be assessed and, if necessary, results will be reported in the clinical study report. Interactions between treatment and the baseline score will be investigated but not included in the model. If interactions are found to be significant, results might have to be presented separately by subgroup. No adjustment for multiplicity will be applied as these analyses will be considered exploratory.

Dataset
 
 LOCF dataset will be used.

Model Results Presentation
 
 Adjusted treatment difference (Q4W IM – Current ART), its 95% CI and the associated p-value. The interaction between treatment and the baseline score will be included in a footnote. Plots of adjusted mean change from baseline (95% CI) for each treatment group, and the adjusted mean difference (95%CI) between the two treatment arms from the model will be generated across visit.

Statistical Analyses

HIVTSQc
 
 Treatment Satisfaction Score (Change) at Week 48

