		Baseline, Day 1	4A	4B ^b	5 ^b	8, 12, 16, 20	24	28, 32, 36, 40	41 ^b	44	48	52	56A	56B ^b	60	64, 72, 80, 88	68, 76, 84, 92			96	Every 4 Weeks After Week 96	Every 12 Weeks After Week 96
Renal, bone, marker analytes (blood/urine) ^p	X									X								X			X	
PBMCs ^q	X																	X			X	
Genetics sample ^r	X																					
Pharmacokinetics – CAB + RPV only																						
PK sampling ^s (S)=Storage only				X	X	X	X	X	X	X	X		X	X	S		X				X	S
Investigational Products																						
Oral CAB and Oral RPV Dispensation ^t	X	X									X	X										
IP accountability (Pill Counts)		X	X									X	X									

Procedure	Screening Visit ^a	Maintenance Phase										Extension Phase								Withdrawal	Follow-up Phase
		Baseline, Day 1	Week																		
			4A	4B ^b	5 ^b	8, 12, 16, 20	24	28, 32, 36, 40	41 ^b	44	48	52	56A	56B ^b	60	64, 72, 80, 88	68, 76, 84, 92	96	Every 4 Weeks After Week 96		
IM treatment administration ^u			X		X	X	X		X	X	X	X	X	X	X	X	X	X	X		
Patient Reported Outcomes^v																					
HAT-QoL (short-form)		X				X				X								X			X
SF-12		X				X				X								X			X
HIV TSQs		X		X		X				X								X			X
HIV TSQc ^w										X											X
ACCEPT		X				X				X								X			X
Reason for Switch ^x		X									X										
Preference ^y										X								X			

Procedure	Screening Visit ^a	Maintenance Phase											Extension Phase						Withdrawal	Follow-up Phase				
		Week																						
		Baseline, Day 1	4A	4B ^b	5 ^b	8, 12, 16, 20	24	28, 32, 36, 40	41 ^b	44	48	52	56A	56B ^b	60	64, 72, 80, 88	68, 76, 84, 92	96			Every 4 Weeks After Week 96	Every 12 Weeks After Week 96		
NRS ^z			X	X			X Wk40 only	X									X							
PIN				X				X		X							X						X	

Follow Up Visit: Conduct approximately 4 weeks after the last dose of IP. Required only if the participant has ongoing AEs or lab abnormalities at the last on-study visit. This visit may be conducted by telephone.

- a. Complete all Screening assessments within 35 days. Participants may begin the Maintenance Phase as soon as all Screening assessments are complete. Participants may be rescreened once and will be assigned a new participant number.
- b. Visits at Weeks 4b, 5, 41, and 56b are only for participants randomized to CAB LA + RPV LA or transitioning from current ART to CAB LA + RPV LA during the Maintenance or Extension Phase, respectively.
- c. Confirmation of eligibility to enter the Maintenance Phase, and eligibility to enter the Extension Phase.

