- n. An overnight fast is preferred; however, a minimum of a 6-hour fast is acceptable.
- o. Only collect if the Withdrawal visit occurs at Week 48, or 96.
- p. Blood sample for renal and bone biomarker assessments: **Renal:** Cystatin C; Retinol Binding Protein (RBP); **Bone:** bone specific alkaline phosphatase, procollagen type 1-N-propeptide, type 1 collagen cross-linked C-telopeptide, osteocalcin, 25 hydroxy-Vitamin D
- q. Whole blood/PBMC collection samples may be used for virologic analyses. PBMCs will be collected at Day 1, Week 96, and Withdrawal if prior to Week 96.
- r. Informed consent for genetic research must be obtained before sample collection
- s. One blood sample for CAB and RPV each to be collected at each PK timepoint. PK samples are to be collected pre-dose during visits requiring IM administration. 2-hour post dose samples also taken at Weeks 4b, 48, 56b, and 96. Pre-dose samples at Weeks 56b, 60, and 2 hour post-dose sample at Week 56b are only for subjects transitioning from Current Art arm to CAB LA + RPB LA. Pre-dose samples are to be collected after review of PK diary at Week 4b and 56b and prior to the final oral dose of CAB + RPV. Additionally, PK samples will be taken during the 1-week post-dose Week 5 and 41 visits. PK window allowed for sample collection; includes 3 to 10 days for 1-week post dose sample (Visits 5 and 41); ±one hour for 2-hour post dose sample (Weeks 4b, 48, 56b, and 96).
- t. Only for Participants entering CAB LA+ RPV LA Oral Treatment
- u. Participants switching to CAB LA + RPV LA will take final dose of oral lead-in regimen in the clinic at The Week 4b visit or Week 56b and begin injections. If possible, injections should be spaced approximately 2 cm from one another and from the site of any previous injection and or any injection site reaction. Bring RPV LA to approximately room temperature prior to injecting. Time and location of injection (right or left) as well as needle length used will be collected in the eCRF. The first injection can be performed as soon as central lab results become available and safety parameters are reviewed.
- v. With the exception of the NRS, all Patient Report Questionnaires/Surveys are recommended to be administered at the beginning of the visit before any other assessments are conducted and prior to administration of the NRS is to be given post injection. Conduct questionnaires/surveys at Withdrawal if occurring prior to Week 96.

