13.7.2.2. Handling of Missing data for Statistical Analysis

Element	Reporting Detail
Snapshot	
 In the Snapshot dataset, subjects without HIV-1 RNA data in the assessment window for the visit of interest (due to missing data or discontinuation of IP prior to the visit window) do not belong to 'HIV-1 RNA < 50 c/mL (or <200 c/mL)'. The nature of this missing data will be further classified in Snapshot summaries as either 'HIV-1 RNA ≥ 50' or 'No Virologic Data at Week X'; Appendix 11: Snapshot Algorithm Details for full details
LOCF	
 In the LOCF dataset, missing values will be carried forward from the previous, non-missing available on-treatment assessment. If the baseline value is missing any missing values until the first non-missing value will remain missing.
Lipid LOCF	
Baseline for Lipids LOCF Analyses:
 
 Last evaluable lipids assessment up to and including the start of IP, where 'evaluable' is defined as: Lipid modifying agents not taken within 12 weeks of the date of assessment and Lipids are collected in a fasting state. Subjects with unevaluable Baseline for Lipids (as defined above) will be excluded from this dataset.

Element	Reporting Detail
	
Post-Baseline:
 
 ● If subjects initiate serum lipid-lowering agents Post-baseline, then the last available fasted On-treatment lipid values prior to the initiation will be used in place of future, observed On-treatment values. ● Imputation at visits with observed on-treatment values will continue even if the subject discontinues the lipid-lowering agent. Missing assessments will not be imputed 
Analyses Evaluated with Lipid LOCF dataset:
 
This dataset will be used to summarize fasting lipids parameters in the following displays:
 
 ● Summary of Chemistry Values by visit ● Summary of Chemistry Change from Baseline by visit ● Summary of TC/HDL ratio Change from Baseline. ● All other displays of lipids (i.e. toxicity tables and NCEP tables) will use observed fasting data, without LOCF imputation

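### LOCF for the key secondary Week 44 HIVTSQs test can carry forward a pre-injection score that only the CAB arm is scheduled to have

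*SAP*

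**What the plan says.** - **Status of the test.** SAP 5.5.2 lists among the key secondary comparisons "Superiority of Q4W IM compared to Current ART respect to change from baseline in HIVTSQs, at Week 44", at a two-sided 5% level. Section 10.6 nevertheless describes the same family of models as exploratory.
- **Dataset.** The 10.6 ANCOVA covers "HIVTSQs total treatment satisfaction score at Week 4b, 24, 44", and for it the "LOCF dataset will be used". Table 7.24 in Appendix 13 repeats this. The HIVTSQs tables without LOCF (7.20 and 7.22) are descriptive.
- **LOCF rule (13.7.2.2).** In this dataset "missing values will be carried forward from the previous, non-missing available on-treatment assessment". The next sentence adds: "If the baseline value is missing any missing values until the first non-missing value will remain missing".
- **Visits.** Table 14 plans HIVTSQs at Day 1 and Weeks 4b, 24 and 44. Footnote b of the schedule (13.2.1) says "Visits at Weeks 4b, 5, 41, and 56b are only for participants randomized to CAB LA + RPV LA", or for those who switch to that regimen in the Extension Phase.
- **What happens at Week 4b.** Footnote u has the last oral lead-in dose and the first injections at this visit. Under footnote v, questionnaires other than the NRS "are recommended to be administered at the beginning of the visit before any other assessments are conducted".
- **Withdrawal forms.** Table 7 and the schedule collect HIVTSQs at withdrawal without restricting it by arm. Section 13.3.4.2 moves such a score to the next planned visit. Table 20 ends on-treatment status in the CAB arm at the later of last injection plus 35 days and last oral dose plus 1 day. In the control arm it ends at ART stop plus 1 day.

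**The concern.** The Week 44 comparison is meant to show whether people on monthly injections are more satisfied than people who stay on their current tablets. A CAB score taken before any injection cannot inform that. Under LOCF it can still stand as the Week 44 value, and for people who stopped soon after injections began. Some of them may have stopped because of the injections.

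The control arm has no scheduled counterpart to Week 4b. Early leavers without a usable withdrawal form are therefore represented differently in the two arms: by a tablet-phase score in CAB, and by zero change or exclusion in control. The trial is open-label and the claim is formal superiority. No planned inferential analysis would show whether that claim depends on the carried values.

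**Working it through.** **1. Who is affected.** The SAP gives no HIVTSQs effect, SD, power or dropout rate, so there is no stated figure to reproduce. The first step is to trace the text for someone who leaves before the Week 24 questionnaire.

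| Leaver before Week 24 | CAB arm | Current ART arm |
|---|---|---|
| Scheduled post-baseline score | Week 4b (oral lead-in) | none |
| Usable on-treatment withdrawal form | moved to Week 24, replaces Week 4b, carried to Week 44 | moved to the next planned visit, carried to Week 44 |
| No usable form | Week 4b score carried to Week 44 | zero change or excluded |

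The arms differ only in the last row. A CAB form can be unusable because it was never completed or because it came after the Table 20 limit. It is also unusable if it falls after the start of long-term follow-up ART, since Table 17 then places it outside Maintenance. A control participant who leaves but keeps taking ART stays on-treatment under Table 20, so a control form is more often usable.

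The control entry in that row is open because 13.7.2.2 points two ways. Only on-treatment values are to be carried, and baseline is pre-treatment. Yet the clause on missing baseline makes sense only if a baseline that is present may be carried.

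**2. Size, on assumed inputs.** From the SAP: N = 570 randomised 1:1, so n = 285 per arm, tested at two-sided 5%. Assumed: f, the share of the CAB arm whose Week 44 value is the carried Week 4b score, and g, the amount in SD by which that score exceeds the value that should stand at Week 44. There is no true difference.

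- SE of the difference = √(2/285) = 0.0838 SD
- Bias = f × g
- One-sided false superiority for CAB = 1 − Φ(1.96 − bias/SE)

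| f | g = 0.5 SD | g = 1 SD |
|---|---|---|
| 1% | bias 0.005, 2.9% | bias 0.010, 3.3% |
| 2% | bias 0.010, 3.3% | bias 0.020, 4.3% |
| 5% | bias 0.025, 4.8% | bias 0.050, 8.6% |
| 10% | bias 0.050, 8.6% | bias 0.100, 22% |

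The nominal value is 2.5%. For f = 5% and g = 1: 0.050/0.0838 = 0.60, and 1 − Φ(1.36) = 8.6%. If the carried score is instead 1 SD too low, the same 5% gives 1 − Φ(2.56) = 0.5%, which works against CAB.

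**3. What dropping Week 4b achieves.** Take SD 7.5 points, so SE = 7.5 × √(2/285) = 0.63. Assume affected participants scored +4 at Week 4b and would score −4 at Week 44, and that the CAB mean over everyone is 0.

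- Week 4b carried, f = 5%: bias 0.05 × 8 = 0.40 points; 0.40/0.63 gives 9.3%.
- The same people excluded: the remaining CAB mean is 0.05 × 4/0.95 = 0.21 points, which gives 5.2%.
- The same people set to zero change: bias 0.05 × 4 = 0.20 points; 0.20/0.63 = 0.32, and 1 − Φ(1.64) = 5.0%.

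Removing the Week 4b score removes roughly half of this bias. The rest comes from assuming that leavers end up below baseline.

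**The case against.** - **One rule, not two.** A reader might infer that the arms are imputed by different rules. Section 13.7.2.2 states a single rule for both; what differs is the visits and on-treatment limits that feed it.
- **Withdrawal scores.** A reader might also infer that control leavers can never have a post-baseline score. They can, because withdrawal forms are collected and slotted in both arms. With injections every 4 weeks and a 35-day limit, a CAB participant who withdraws at the next scheduled visit has a usable form that displaces Week 4b. This stands, and it makes the affected group narrow.
- **Redaction.** Section 10.4 refers missing health-outcome data to 13.6.6, whose HIVTSQs text is removed. A further rule there cannot be excluded, although 10.6, 13.7.2.2 and Table 7.24 all name LOCF.
- **Timing.** Completing the questionnaire before the injection is recommended, not required. A Week 4b score completed as recommended is still a tablet-phase score.
- **Existing checks.** Descriptive tables without LOCF (7.20, 7.22) would show whether carrying forward moves the means, but they give no test or adjusted estimate.
- **Remedy.** A repeated-measures model on Weeks 24 and 44 has no post-baseline data for these leavers, so it largely reproduces the mean of those who stayed. This stands and shapes the fix.
- **Other questionnaires.** The argument does not extend to ACCEPT, SF-12 or HATQoL. None has a planned visit that is CAB-only during Maintenance.

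**Conclusion.** The point holds in a limited form. As written, the SAP allows a pre-injection score that only the CAB arm is scheduled to have to serve as Week 44 satisfaction with injections. This happens for CAB participants who leave between Week 4b and the Week 24 questionnaire without a usable on-treatment withdrawal score. The SAP also leaves open how comparable control participants are handled, and it plans no inferential analysis without LOCF.

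The size cannot be read from the document. On the assumptions above the effect is small at 1% to 2% affected (about 3% to 4% one-sided with a 1 SD gap) and becomes material at about 5% (about 9%). Both the share and the gap are assumed, and the direction depends on leavers' carried scores being higher than the values that should stand at Week 44. A reader might infer that a superiority result would be an artefact of LOCF; nothing in the SAP supports that.

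The matter should be settled before analysis, because the comparison is a formal key secondary one and the change costs little.

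**What to change.** For HIVTSQs only:

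1. State that the Week 4b score is not carried to Week 24 or Week 44.
2. State whether baseline is carried forward, identically in both arms, and remove the tension in 13.7.2.2.
3. Add two inferential analyses of Week 44 without LOCF. One is a repeated-measures model on Weeks 24 and 44 in both arms, with treatment, visit, their interaction and the covariates already listed in 10.6. The other sets participants who stopped the assigned regimen to zero change. The second is needed because the first does not address informative dropout. Zero change is itself only a partial answer if leavers end up below baseline, so the two should be read together.
4. While editing, reconcile two related places. Section 10.6 plans a between-arm contrast at Week 4b, where the control arm has no scheduled visit. It also calls these analyses exploratory, while 5.5.2 makes Week 44 HIVTSQs key secondary.

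The cost is a few lines of SAP text and two extra models on data already collected. The CAB estimate may come out slightly less favourable.

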
transition to CAB LA + RPV LA in the Extension Phase
	
through Week 96
 
 • Absolute values and change from Baseline in plasma HIV-1 RNA over time including Week 96 • Absolute values and changes from Baseline in CD4+ cell counts over time including Week 96 • Incidence of disease progression (HIV-associated conditions, acquired immunodeficiency syndrome [AIDS] and death) • Incidence and severity of AEs and laboratory abnormalities over time including Week 96 • Proportion of participants who discontinue treatment due to AEs over time including Week 96 • Absolute values and changes in laboratory parameters over time including Week 96 • Incidence of treatment emergent genotypic and phenotypic resistance to CAB, RPV, and other on study ART through Week 96

To assess the acceptance of pain and injection site reactions following injections
	
 • Change from Week 5 in Dimension scores (“Bother of ISRs”, “Leg movement”, “Sleep”, and “Injection Acceptance”) and individual item scores assessing pain during injection, anxiety before and after injection, willingness to be injected in the future and overall satisfaction with mode of administration over time using the Perception of iNjection questionnaire (PIN) • Proportion of participants considering pain and local reactions following injection to be extremely or very acceptable based on the acceptability score over time using the Perception of iNjection questionnaire (PIN)

To assess degree of health-related quality of life (HRQoL)
	
 • Change from Baseline in HR QoL using the HIV/AIDS-targeted quality of life questionnaire (HAT QoL) short form at Week 24, Week 48, Week 96 (or Withdrawal).

To assess the health status
	
 • Change from Baseline in health status at Week 24, Week 48, and Week 96 (or Withdrawal) using the 12-item Short Form Survey (SF-12).

To assess treatment satisfaction of CAB LA + RPV LA compared to
	
 • Change from baseline in total “treatment satisfaction” score, and individual items scores of the HIVTSQs at

Objectives	Endpoints
continuation of current ART	Weeks 4b, 24, 44, 96 (or Withdrawal) 
 Change in treatment satisfaction over time using the HIVTSQc at Week 48 (or Withdrawal)

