10.5. Statistical Analyses / Methods

[Table 7](#) provides an overview of the planned analyses. Details of the planned displays are provided in [Appendix 13: List of Data Displays](#) and will be based on GSK Data Standards and statistical principles.

Table 7 Overview of Planned Health Outcome Analyses

Endpoints	Absolute								Change from Baseline							
	Stats Analysis			Summary		Individual			Stats Analysis			Summary		Individual		
	T	F	L	T	F	F	L	T	F	L	T	F	F	L		
Perception of Injection (PIN) at Week 5, 41, 48, 96																
Individual Item Scores				Y			Y									
Domain of 'Bother from injection site reactions', 'Leg movement', 'Sleep', 'Acceptability'	Y ^[4]			Y			Y				Y					
Health-related quality of life (HATQoL) at baseline, wk24, 48, 96, withdrawal																
Individual Item Scores				Y			Y									
Subscale of Life satisfaction, HIV medication, and disclosure worries				Y			Y	Y	Y ^[1]		Y					
Health Status (SF-12) at Baseline, wk24, 48, 96)																
Individual Item Scores				Y			Y									
Total Score, Mental health component (MCS) and physical component summary (PCS) ^[2]				Y			Y	Y	Y ^[1]		Y					
Treatment Satisfaction Score (HIVTSQs) at Baseline, Week 4b, 24, 44, 96, withdrawal																
Individual Item Scores				Y			Y									
Individual Item Scores by subgroup ^[3]				Y												
Treatment Satisfaction Score				Y			Y	Y	Y ^[1]		Y					
Treatment Satisfaction Score Change (HIVTSQc) at 48, withdrawal																
Individual Item Scores	Y			Y			Y									
Treatment Satisfaction Score Change	Y			Y			Y									

Endpoints	Absolute								Change from Baseline							
	Stats Analysis			Summary		Individual			Stats Analysis			Summary		Individual		
	T	F	L	T	F	F	L	T	F	L	T	F	F	L		
Treatment Acceptance (ACCEPT) at Baseline, week 8, 24, 48, 96, withdrawal																
proportion of Individual item score				Y			Y									
Acceptance/General Dimension Score				Y			Y	Y	Y ^[1]		Y					
Tolerability of injection (NRS) at week 4b, week 5, 40, 41, 96 within Q4W IM arm																
proportion of Individual item score				Y			Y									
Tolerability Score (Q4W IM only)				Y			Y				Y					
Treatment Preference at Week 48 (for both treatment arms) and Week 96 (for Current ART only)																
Treatment: Monthly injection vs Daily oral ART				Y			Y									
Willingness to switch at Baseline (Q4W IM), and Week 52 (Current ART)																
Willingness to switch				Y			Y									

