
Model Specification
 
 An analysis of variance (ANOVA) model will be used with covariates: treatment, age (<50, ≥ 50 years old), baseline third agent, sex at birth, and race (white, non-white) (as described in Section 5.4)

Dataset
 
 The observed case (OC) dataset uses only the data that is available at Week 48, with no imputation for missing values.

Model Results Presentation
 
 Adjusted means, 95% CI, and associated P value will be presented for the treatment difference (Q4W IM –Current ART). Adjusted point estimates will be derived as LSMEAN S using the observed margins (OM) option in modelling.

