- w. HIV TSQ (c) to be administered at Week 48 to LA injection arm only
- x. "Reason for switch" will be administered prior to randomization at Day 1. At Week 52, "Reason for Switch" will be given only to participants randomized to the "Current ART" arm.
- y. Preference" question to be administered at Week 48 to patients randomized to CAB LA + RPV LA arm, and at Week 96 to patients randomized to the "current ART arm" who switched to CAB LA + RPV LA at the end of maintenance phase.
- z. NRS will be administered on injection visits approximately 30-60 minutes following injections. Participant should record the maximum level of pain experienced with the most recent injections.

Note: BP – Blood pressure, HR – Heart Rate, HDL – High Density Lipoprotein, LDL – Low Density Lipoprotein, PT Prothrombin Time, PTT Partial Thromboplastin Time, INR International normalized ratio

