7.25.	ITT-E	Shell THO2	Proportion of Subjects with HIV-Treatment Satisfaction Questionnaire Individual Item Scores change) (Maintenance phase)		WK48
7.26.	ITT-E	Shell THO1	Summary of HIV-Treatment Satisfaction Questionnaire in Treatment Satisfaction Score Change)(Maintenance phase)		WK48
7.27.	ITT-E	Shell THO5	Statistical Analysis of HIV-Treatment Satisfaction Questionnaire in Treatment Satisfaction Score Change at Week 48 ())(Maintenance phase)	ANOVA for analysis	WK48

Health Outcomes : Tables					
No.	Population	IDSL / TST ID / Example Shell	Title	Programming Notes	Deliverable
Treatment Acceptance (ACCEPT)					
7.28.	ITT-E	Shell THO2	Proportion of Subjects with Treatment Acceptance Questionnaire(ACCEPT) Individual Item Scores by Visit - LOCF)(Maintenance phase)		WK48
7.29.	ITT-E	Shell THO1	Summary of Acceptance/General Dimension Score (ACCEPT Questionnaire) by Visit (Maintenance phase)		WK48
7.30.	ITT-E	Shell THO1	Summary of Acceptance/General Dimension Score (ACCEPT Questionnaire) by Visit - LOCF(Maintenance phase)		WK48
7.31.	ITT-E	Shell THO1	Summary of Change from Baseline in Acceptance/General Dimension Score (ACCEPT Questionnaire) by Visit (Maintenance phase)		WK48
7.32.	ITT-E	Shell THO1	Summary of Change from Baseline in Acceptance/General Dimension Score (ACCEPT Questionnaire) by Visit - LOCF(Maintenance phase)		WK48
7.33.	ITT-E	Shell THO3	Statistical Analysis of Change from Baseline in Acceptance/General Dimension Score (ACCEPT Questionnaire) by Visit – LOCF (Maintenance phase)	ANCOVA for analysis	WK48
Tolerability of Injection, NRS (for Q4W IM)					
7.34.	ITT-E	Shell THO2	Proportion of Subjects with Tolerability of Injection (NRS) Individual item scores by Visit - LOCF)(Maintenance phase)		WK48
7.35.	ITT-E	Shell THO9	Summary of Tolerability of Injection(NRS) scores by Visit (Maintenance phase)		WK48
7.36.	ITT-E	Shell THO9	Summary of Tolerability of Injection(NRS) scores by Visit - LOCF) (Maintenance phase)		WK48
7.37.	ITT-E	Shell THO9	Summary of Tolerability of Injection (NRS) by Visit - Change from Week 4B Scores)(Maintenance phase)		WK48

Health Outcomes : Tables					
No.	Population	IDSL / TST ID / Example Shell	Title	Programming Notes	Deliverable
7.38.	ITT-E	Shell THO9	Summary of Tolerability of Injection (NRS) by Visit - Change from Week 4B Scores - LOCF)(Maintenance phase)		WK48
Preferences (Dichotomous preference question)					
7.39.	ITT-E	Shell THO8	Treatment Preference at Week 48 (Maintenance phase)		W48
Willingness to switch					

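### The SAP contradicts itself on which arm completes HIVTSQc at Week 48: the schedule gives it to the injection arm only, the analysis section plans a between-arm ANOVA

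*SAP*

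**What the plan says.** **Analysis side**

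- SAP Section 2.2 places HIVTSQc under a secondary objective that compares satisfaction with continued current ART. The endpoint reads "Change in treatment satisfaction over time using the HIVTSQc at Week 48 (or Withdrawal").
- Table 7 in Section 10.5 has a block headed "Treatment Satisfaction Score Change (HIVTSQc) at 48, withdrawal" and marks a formal statistical analysis for the item scores and for the score itself.
- Section 10.6 specifies the model: "An analysis of variance (ANOVA) model will be used with covariates: treatment, age" group, baseline third agent, sex at birth and race. For the data: "The observed case (OC) dataset uses only the data that is available at Week 48, with no imputation for missing values". For the output, the "associated P value will be presented for the treatment difference", defined as Q4W IM minus Current ART.
- Display 7.27 in Section 13.13.9 is titled "Statistical Analysis of HIV-Treatment Satisfaction Questionnaire in Treatment Satisfaction Score Change at Week 48". Its population is ITT-E, its programming note calls for ANOVA, and it carries no arm restriction.

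**Collection side**

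- The schedule of events in Section 13.2.1 attaches footnote w to the HIVTSQc row: "HIV TSQ (c) to be administered at Week 48 to LA injection arm only".
- The same row also has a Withdrawal entry, and footnote v asks for questionnaires at withdrawal before Week 96. Footnote w does not mention withdrawal.

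**The concern.** A between-arm difference needs data from both arms. Section 10.6 reports one for HIVTSQc, while the collection rule reproduced in the same document gives the questionnaire at that visit to one arm. A programmer cannot build display 7.27 from this without a decision that the SAP does not make.

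Two things are at stake. If the comparison was intended and sites followed footnote w, the Current ART questionnaires were not collected and cannot be recovered. If the instrument was meant for the injection arm only, the specified output either fails or runs on whatever stray Current ART values reach the dataset. A choice made after the data are seen would be post hoc.

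**Working it through.** The SAP gives no sample size or power for HIVTSQc, so there is no figure of its own to reproduce. The check is whether the Section 10.6 model can be fitted under each reading.

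**Inputs**

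- From Section 2.3: N = 570 randomized 1:1, so 570 / 2 = 285 per arm.
- From Section 10.6: treatment (2 levels), age (2), third agent (3), sex (2), race (2).
- Assumed: everyone in an arm that receives the questionnaire completes it. Covariate frequencies are illustrative and do not affect the rank result for an empty control arm. For power only, a true difference of 0.3 SD, two-sided 5%.

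**Step 1: model columns.** Intercept 1 + treatment 1 + age 1 + third agent 2 + sex 1 + race 1 = 7.

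**Step 2: footnote w taken literally (285 injection arm, 0 Current ART).** Every row has treatment = 1, so the treatment column is identical to the intercept. The rank is 6 with 7 columns. The treatment effect is not estimable, and neither are its CI and p-value.

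**Step 3: both arms complete it (285 and 285).** The rank is 7 of 7. Ignoring covariates, in SD units:

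SE = √(1/n₁ + 1/n₀) = √(1/285 + 1/285) = 0.084

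With the covariates it is 0.085. Power = Φ(0.3/0.084 − 1.96), about 95%. The ANOVA is then a sound analysis.

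**Step 4: the withdrawal route.** Section 13.3.4.2 slots a withdrawal questionnaire by identifying the last nominal visit at which that instrument was completed and then moving to the next planned one. Table 14 gives HIVTSQc a single nominal visit in the Maintenance Phase, Week 48, so there is no earlier visit to start from. The rule does not say whether a withdrawal HIVTSQc becomes a Week 48 value. If it did, the model would run. The control counts below are assumed, because the SAP gives none:

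| Current ART values | SE (SD units), with covariates | Power at 0.3 SD |
|---|---|---|
| 0 | not estimable | none |
| 5 | 0.46 | 10% |
| 15 | 0.27 | 20% |
| 30 | 0.19 | 35% |
| 285 | 0.085 | 95% |

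Precision is the lesser problem in the middle rows. Those Current ART values would all come from people who left early, so the contrast would no longer compare the randomized groups.

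**The case against.** The strongest reply is that footnote w may be the mistake. It is one line in a schedule. Against it stand a comparative objective, the Table 7 marks, a full model specification, and a display with no arm limit in a list that heads the NRS displays as Q4W only. The HIVTSQc text in Section 13.6.6 is redacted and might state the arm, as the readable preference entry there does. The protocol is not at hand either. All of this stands. It means that one cannot say which text is wrong, but it does not remove the conflict.

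A reader might infer four stronger things that the document does not support:

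- **That the comparison simply cannot be done, with 0 of about 285 controls measured.** This holds only if footnote w is right, and only for the Week 48 visit.
- **That Table 14 settles it, because PIN and NRS are labelled Q4W there and HIVTSQc is not.** The treatment preference row is also unlabelled, although footnote y gives that question at Week 48 to the injection arm only.
- **That control drop-outs will contaminate the result.** The slotting rule leaves this undetermined.
- **That the satisfaction claim is at risk.** The key secondary comparison in Section 5.5.2 uses HIVTSQs at Week 44. HIVTSQc is in neither the key secondary nor the supportive list there.

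One might also say that an empty control arm would show up at once in the output. That is true when there are no control values at all. With a few withdrawal values the model would run without any warning.

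**Conclusion.** The contradiction is real and lies wholly within the SAP. Section 10.6 and display 7.27 need Current ART data that footnote w says are not collected at Week 48, and no readable text reconciles them. If footnote w is correct, the planned treatment difference is not estimable from Week 48 visit data, and any estimate would rest on control withdrawals. If footnote w is wrong, the ANOVA is sound and the schedule needs correcting.

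The consequence is limited to one listed secondary endpoint. The primary endpoint, the key secondary comparisons and the safety analyses do not depend on it. It should be fixed, but it is not critical. The SE and power figures rest on full completion, assumed covariate frequencies, an assumed 0.3 SD effect and assumed withdrawal counts. The rank result for an empty control arm does not depend on these.

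**What to change.** Decide before the Week 48 data cut which arm or arms complete HIVTSQc, and align the texts.

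- **If both arms complete it:** correct footnote w and keep the ANOVA and display 7.27 as they are.
- **If only the injection arm completes it:** remove the treatment term, the difference and the p-value from Section 10.6 and display 7.27. Mark HIVTSQc as Q4W only in Tables 7 and 14. Report the injection-arm mean with its 95% CI, labelled non-comparative, and leave the between-arm satisfaction question to HIVTSQs at Week 44. A test against a no-change value should not be added from the readable text, because the scoring is redacted.
- **In either case:** state in Section 13.3.4.2 whether a withdrawal HIVTSQc counts as a Week 48 value, since the present rule has no starting visit for this instrument.

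The cost is a few lines of SAP wording and one display shell, or one footnote in the schedule. If both arms were intended and sites have followed footnote w, Current ART questionnaires already missed cannot be recovered, so the decision should come early.
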